#### For Patients with Non-Measurable Disease (i.e., Non-Target Disease)

Non-Target Lesions	New Lesions	Overall Response
--------------------	-------------	------------------

CR	No	CR
Non-CR/non-PD	No	Non-CR/non-PD*
Not all evaluated	No	not evaluated
Unequivocal PD	Yes or No	PD
Any	Yes	PD

\* ‘Non-CR/non-PD’ is preferred over ‘stable disease’ for non-target disease since SD is increasingly used as an endpoint for assessment of efficacy in some trials so to assign this category when no lesions can be measured is not advised

#### 10.1.5 Duration of Response

Duration of overall response: The duration of overall response is measured from the time measurement criteria are met for CR or PR (whichever is first recorded) until the first date that recurrent or progressive disease is objectively documented (taking as reference for progressive disease the smallest measurements recorded since the treatment started).

The duration of overall CR is measured from the time measurement criteria are first met for CR until the first date that progressive disease is objectively documented.

Duration of stable disease: Stable disease is measured from the start of the treatment until the criteria for progression are met, taking as reference the smallest measurements recorded since the treatment started, including the baseline measurements.

#### 10.1.6 Progression-Free Survival

**PFS is defined as the duration of time from start of treatment to time of progression or death, whichever occurs first.**

#### 10.1.7 Response Review

All responses will be reviewed by PI and, simultaneous review of the patients’ files and radiological images.

### 11. DATA REPORTING / REGULATORY REQUIREMENTS

#### 11.1 Data Safety Monitoring Plan

Investigator/Sub-investigators, regulatory, CRS management, clinical research coordinators, clinical research associates, data managers, and clinic staff meet monthly in disease center Data Safety Monitoring Boards (DSMB) to review and discuss study data to include, but not limited to, the following:

- serious adverse events
- subject safety issues
- recruitment issues
- accrual

- protocol deviations
- unanticipated problems
- breaches of confidentiality

All toxicities encountered during the study will be evaluated on an ongoing basis according to the NCI Common Toxicity Criteria version 4. All study treatment associated adverse events that are serious, at least possibly related and unexpected will be reported to the IRB. Any modifications necessary to ensure subject safety and decisions to continue, or close the trial to accrual are also discussed during these meetings. If any literature becomes available which changes the risk/benefit ratio or suggests that conducting the trial is no longer ethical, the IRB will be notified in the form of an Unanticipated Problem submission and the study may be terminated.

All study data reviewed and discussed during these meetings will be kept confidential. Any breach in subject confidentiality will be reported to the IRB in the form of an Unanticipated Problem submission. The summaries of these meetings are forwarded to the UPCI DSMC which also meets monthly following a designated format.

For all research protocols, there will be a commitment to comply with the IRB's policies for reporting unanticipated problems involving risk to subjects or others (including adverse events). DSMC progress reports, to include a summary of all serious adverse events and modifications, and approval will be submitted to the IRB at the time of renewal.

Protocols with subjects in long-term (survival) follow-up or protocols in data analysis only, will be reviewed twice a year rather than monthly by the disease center DSMB.

Both the UPCI DSMC as well as the individual disease center DSMB have the authority to suspend accrual or further investigate treatment on any trial based on information discussed at these meetings.

All records related to this research study will be stored in a locked environment. Only the researchers affiliated with the research study and their staff will have access to the research records.

## **11.2 Quality Control and Quality Assurance**

Independent monitoring of the clinical study for protocol and Guidelines on Good Clinical Practice compliance will be conducted periodically (i.e., at a minimum of annually) by qualified staff of the Education and Compliance Office – Human Subject Research, Research Conduct and Compliance Office, University of Pittsburgh.

The Investigator (i.e., the study site principal investigator) and the University of Pittsburgh and University of Pittsburgh Medical Center will permit direct access of the study monitors and appropriate regulatory authorities to the study data and to the corresponding source data and documents to verify the accuracy of this data.

### **11.3 Data Handling and Record-Keeping**

The Investigator (i.e., the study site principal investigator) will maintain records in accordance with Good Clinical Practice.

The investigator will retain the specified records and reports for up to 2 years after the marketing application is approved for the investigational drug; or, if a marketing application is not submitted or approved for the investigational drug, until 2 years after investigations under the IND have been discontinued and the FDA so notified.

### **11.4 Institutional Review Board (IRB) Approval**

The investigator (i.e., the study site principal investigator) will obtain, from the University of Pittsburgh Institutional Review Board (IRB), prospective approval of the clinical protocol and corresponding informed consent form(s); modifications to the clinical protocol and corresponding informed consent forms, and advertisements (i.e., directed at potential research subjects) for study recruitment, if applicable.

The only circumstance in which a deviation from the current IRB-approved clinical protocol/consent form(s) may be initiated in the absence of prospective IRB approval is to eliminate an apparent immediate hazard to the research subject(s). In such circumstances, the investigator will promptly notify the University of Pittsburgh IRB of the deviation.

The University of Pittsburgh IRB operates in compliance with FDA regulations at [21 CFR Parts 50](#) and [21 CFR 56](#), and in conformance with applicable International Conference on Harmonization (ICH) Guidelines on Good Clinical Practice.

### **11.5 Ethical and Scientific Conduct of the Clinical Study**

The clinical study will be conducted in accordance with the current IRB-approved clinical protocol; ICH Guidelines on Guidelines on Good Clinical Practice; and relevant policies, requirements, and regulations of the University of Pittsburgh IRB, University of Pittsburgh and University of Pittsburgh Medical Center, Commonwealth of Pennsylvania, and applicable federal agencies.

### **11.6 Subject Informed Consent**

The investigator (i.e., the study site principal investigator) will make certain that an appropriate informed consent process is in place to ensure that potential research subjects, or their authorized representatives, are fully informed about the nature and objectives of the clinical study, the potential risks and benefits of study participation, and their rights as research subjects. The investigator, or a sub-investigator, will obtain the written, signed informed consent of each subject, or the subject's authorized representative, prior to performing any study-specific procedures on the subject. The date and time that the subject, or the subject's authorized representative, signs the informed consent form and a narrative of the issues discussed during the informed consent process will be documented in the subject's case history. The investigator, or

sub-investigator, will retain the original copy of the signed informed consent form, and a copy will be provided to the subject, or to the subject's authorized representative.

The investigator will make certain that appropriate processes and procedures are in place to ensure that ongoing questions and concerns of enrolled subjects are adequately addressed and that the subjects are informed of any new information that may affect their decision to continue participation in the clinical study. In the event of substantial changes to the clinical study or the risk-to-benefit ratio of study participation, the investigator will obtain the informed consent of enrolled subjects for continued participation in the clinical study.

## **12. STATISTICAL CONSIDERATIONS**

### **12.1 Data Analysis Plan**

#### **12.1.1 Primary objective**

Evaluate the progression-free survival (PFS) of patients with advanced biliary cancer who had failed first-line chemotherapy when receiving regorafenib. The progression-free survival function will be estimated by the Kaplan-Meier method, with a 90% confidence interval. The estimated median PFS will be derived from the estimated progression free survival function. The null hypothesis that the median PFS is 2.0 months or less (see Justification of Design, below) will be tested using the two-sided 80% confidence interval around the median PFS. If the left side of the confidence interval does not include two months, the null hypothesis will be rejected ( $\alpha=0.10$ ).

#### **12.1.2 Secondary objectives**

- Overall response rate (ORR), including complete and partial response. The ORR at four months will be estimated with an exact 90% binomial confidence interval.
- Overall survival (OS). The overall survival function will be estimated by the Kaplan-Meier method, with a 90% confidence interval.
- DCR (disease control rate) as ORR plus stable disease (SD)
- Measurable changes in biomarkers (CA19-9 and CEA), in patients that were elevated at the time of registration. The means and standard deviation of both markers will be estimated at before and after treatment. The null hypothesis of no treatment effect will be tested using a paired-comparison t-test ( $\alpha=0.10$ ), or a rank sum test if there is evidence of significant non-normality in the differences.
- Evaluation of safety and associated toxicities. Toxicities will be tabulated by grade and type.

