Study design	Patients with advanced and metastatic biliary tract adenocarcinoma (cholangiocarcinoma) who had been treated with and failed first-line chemotherapy will be treated with regorafenib (120 mg) orally once daily 21 days (3 weeks) on and 7 days (1 week) off in the 28-day (4-week) cycle.
Type of control	Single arm uncontrolled

Number of subjects	Maximum of 37 patients.
Plan for statistical analysis	
There will be no stratification. OR will be estimated at end of trial with 95% exact binomial confidence intervals. PFS and OS will be estimated by the Kaplan-Meier method, with appropriate 90% confidence intervals. Toxicity events will be tabulated. Change in CA19-9 and CEA will be characterized by their mean changes, with a nonparametric CDF-based 90% confidence interval. The study will have 83% power (using a one-sided test at <math>\alpha=0.10</math>) to reject the null hypothesis (PFS<2.0 months) if the true median PFS is at least 3.5 months.

Schema:

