### 1.2 Secondary Objectives

- Overall response rate (ORR), including complete and partial response, and disease control rate (DCR)
- Overall survival (OS)
- Measurable changes in biomarkers [CA19-9 and CEA], in patients that were elevated at the time of study entry.
- Evaluation of safety and associated toxicities

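### The CA19-9/CEA paired test in Section 12.1.2 is labelled a test of treatment effect, but in an uncontrolled trial it tests only zero mean change from baseline

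*Combined protocol and SAP*

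**What the plan says.** Section 12.1.2 restricts the marker analysis to CA19-9 and CEA "in patients that were elevated at the time of registration". It then states that "The means and standard deviation of both markers will be estimated at before and after treatment", and that "The null hypothesis of no treatment effect will be tested using a paired-comparison t-test", with alpha 0.10 and a rank sum test as the fallback if the differences are clearly non-normal. It does not give the sidedness, the scale (raw or log) or the visit that counts as after treatment.

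Other parts of the protocol are more modest. Section 1.2 lists the objective as "Measurable changes in biomarkers [CA19-9 and CEA], in patients that were elevated at the time of study entry". The synopsis plans only description: "Change in CA19-9 and CEA will be characterized by their mean changes, with a nonparametric CDF-based 90% confidence interval". The claim about treatment effect appears in Section 12.1.2 alone. The synopsis gives the type of control as "Single arm uncontrolled".

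**The concern.** A paired before/after test takes zero mean change as its null. Whether zero change means no treatment effect depends on what the markers would do under an inactive drug, and this design has no arm that shows it.

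The documents give two reasons to doubt that the answer is zero, and they point in opposite directions.

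- **Upward.** Patients have failed first-line chemotherapy. Section 2.1 puts second-line median PFS or TTP at about 1.6 to 2.3 months, and Section 12.1.1 sets up "The null hypothesis that the median PFS is 2.0 months or less". The last scheduled marker draw is at the End of Treatment visit, about 28 days after the last dose, and Section 3.3 makes progression a mandatory reason to stop. Many late samples would therefore be taken after progression.
- **Downward.** Only patients with a raised marker at entry are analysed. A group chosen for high values tends to have lower values on repeat measurement, even if nothing has changed. The Study Calendar shows no marker draw at screening, so the sample that selects the patient is probably also the baseline in the paired difference.

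At stake is a report that regorafenib had, or lacked, an effect on the markers, with an error rate of 0.10 attached. The design cannot support either statement.

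**Working it through.** **Inputs from the documents.** Alpha 0.10 (Section 12.1.2); no control (synopsis); maximum of 37 patients; median PFS 2.0 months under the null and 3.5 under the alternative (Section 12.2).

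**Assumptions, because the documents are silent.** Number with raised markers n = 12 to 37; untreated mean change δ from 0 to 0.5 SD of the paired difference; normal differences; two-sided test unless stated.

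**Step 1: reproduce the stated alpha.** The statistic is t = mean change / (SD/√n). It rejects when |t| exceeds the 0.95 quantile of t with n−1 degrees of freedom (1.711 for n = 25). At δ = 0 the rejection probability is 0.05 + 0.05 = 0.10. The plan's alpha is therefore right for zero mean change.

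**Step 2: inactive drug with an untreated rise.** The statistic is now noncentral t with noncentrality δ√n. For n = 25 and δ = 0.3 this is 0.3 × 5 = 1.5. The probability of rejecting is 0.426 (rise) + 0.001 (fall) = 0.427.

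| Untreated rise (SD) | n = 12 | n = 25 | n = 37 |
|---|---|---|---|
| 0 | 0.10 | 0.10 | 0.10 |
| 0.1 | 0.12 | 0.14 | 0.16 |
| 0.2 | 0.17 | 0.26 | 0.33 |
| 0.3 | 0.26 | 0.43 | 0.56 |
| 0.5 | 0.49 | 0.78 | 0.91 |

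Nearly all of the excess is in the direction of a marker rise. If the test is read as one-sided for a fall, the n = 25, δ = 0.3 case rejects with probability 0.003, so the inflation needs a two-sided reading.

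**Step 3: a drug that only slows growth.** Take n = 25 and a drug that halves the untreated rise.

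- From 0.30 to 0.15 SD: a significant fall has probability 0.009 two-sided or 0.022 one-sided, and a significant rise 0.18.
- From 0.10 to 0.05 SD: a significant fall has probability 0.030 two-sided or 0.063 one-sided.

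These are below the nominal 0.05 and 0.10, although the drug works. They are not zero.

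**Step 4: the opposite bias.** Let a fraction f of 37 patients have a raised marker (n = 37f, rounded down), and let ρ be the test-retest correlation; both are assumed. With no true change, the expected paired difference in between-patient SDs is −(1−ρ)·φ(z)/f, where z is the cut-off that leaves a fraction f above it. For f = 0.7 and ρ = 0.9, φ(z)/f = 0.497 and the difference is −0.1 × 0.497 = −0.050. Its SD is about 0.44, so the shift is about −0.11 SD. With n = 25 a false significant fall then has probability about 0.14 two-sided or 0.23 one-sided. Over ρ = 0.8 to 0.95 and f = 0.5 to 0.9 the range is 0.07 to 0.28 two-sided (nominal 0.05) and 0.13 to 0.42 one-sided (nominal 0.10).

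Steps 2 and 4 pull against each other, and nothing in the documents says which dominates.

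**The case against.** The strongest reply is that the numbers depend on inputs the plan does not contain. No marker kinetics, SD, scale, sidedness or post-treatment visit is given, and the fallback matters. Suppose the rule is followed literally: raw differences, a normality check at 0.05, then an unpaired rank sum test. Simulation with n = 20, SD of log change 0.6 to 1.5 and baseline log-SD 1.0 to 2.0 finds the differences non-normal in at least 85% of runs. Rejection as a rise for an inactive drug is then about 0.02 to 0.48 if the mean log rise is 3·ln(1.2) = 0.55, and 0.00 to 0.07 if it is ln(1.2) = 0.18. A t-test on log changes would give 0.99 to 0.47 and 0.37 to 0.15. This part of the reply stands, so no single inflation figure can be claimed.

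Two stronger readings are tempting, and the documents support neither.

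- *An inactive drug will usually reject.* This needs a large drift relative to SD and a two-sided paired test. The documents state neither, and the rejections would show marker rises, which nobody would read as benefit.
- *A drug that only slows growth can never look favourable.* Step 3 shows that this is unlikely, not impossible, and selection on raised baselines makes an apparent fall more likely.

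It is also fair to say that the objective and the synopsis already speak of change, that Section 10.1.3 bars markers alone from defining response, and that nothing in the PFS test or stopping provisions uses this result. That limits the consequence. It does not remove the mismatch in Section 12.1.2, which is the only section that names a hypothesis for the markers.

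**Conclusion.** The point holds as a mismatch between the stated null and the tested null. The paired test at 0.10 tests zero mean within-patient change. Calling that no treatment effect requires a zero untreated mean change, which the documents give reason to doubt in both directions. Whatever the test shows, it cannot by itself establish or exclude a treatment effect, and alpha 0.10 does not apply to the null as written.

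This conclusion rests only on the absence of a control arm and on the plan's own description of its patients. The probabilities above rest on assumed drift, correlation, scale and sidedness, and are illustrative. The endpoint is secondary; the PFS test and its stated 83% power do not depend on it. The wording should still be corrected, because it invites a conclusion that the design cannot deliver.

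**What to change.** In Section 12.1.2:

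1. Replace the stated null with: *The null hypothesis of no mean change from baseline.*
2. Add: *Because the trial is uncontrolled and patients are selected for elevated baseline markers, neither a decline, a rise nor a non-significant change is by itself evidence for or against a treatment effect.*
3. Make the mean change with its 90% interval, as in the synopsis, the main marker result.

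Do not change to a one-sided test for a decrease at 0.10. That would put all of the alpha in the tail exposed to regression to the mean, where Step 4 gives a false fall of 0.13 to 0.42 against 0.07 to 0.28 two-sided.

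The cost is wording only, with no added patients, samples or visits. The trial gives up a formal treatment-effect claim on a secondary marker endpoint.

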#### 10.1.4.3 Evaluation of Best Overall Response

The best overall response is the best response recorded from the start of the treatment until disease progression/recurrence (taking as reference for progressive disease the smallest measurements recorded since the treatment started). The patient's best response assignment will depend on the achievement of both measurement and confirmation criteria.

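### The non-normal fallback for the paired CA19-9 and CEA comparison is named as a rank sum test, and the response rate has two different confidence levels

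*Combined protocol and SAP*

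**What the plan says.** For the tumour markers, Section 12.1.2 restricts the analysis to patients whose markers were raised at baseline ("in patients that were elevated at the time of registration"; Section 1.2 has the same restriction). It then describes a before/after comparison within patients: "The means and standard deviation of both markers will be estimated at before and after treatment". The test is paired: "The null hypothesis of no treatment effect will be tested using a paired-comparison t-test", at α = 0.10 with sidedness not stated. The alternative is "or a rank sum test if there is evidence of significant non-normality in the differences". The Synopsis names no marker test. It describes only mean changes with a nonparametric 90% interval. The signed-rank test is not mentioned anywhere in the document.

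For the response rate, the Synopsis says "OR will be estimated at end of trial with 95% exact binomial confidence intervals". Section 12.1.2 says "The ORR at four months will be estimated with an exact 90% binomial confidence interval". Section 10.1.4.3 defines best response without a four-month limit: "The best overall response is the best response recorded from the start of the treatment until disease progression/recurrence".

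**The concern.** The rank sum (Mann-Whitney) test compares two independent samples. Here each patient contributes one value to each sample, so the independence on which its null distribution rests does not hold. The trigger for the fallback is non-normality of the differences, and only a paired analysis has differences to examine. The name and its context therefore point to different tests. An analyst who follows the text literally would run a test whose true level is not the stated 0.10. The fallback could well be used if the markers are skewed, which is an assumption because the document gives no distribution.

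The response-rate problem is a plain contradiction: one secondary endpoint has two confidence levels, and nothing says that two intervals are intended. As written, the choice could be made after the data are seen. The time point is also unclear. The Synopsis phrase may describe only when the analysis is run, and Section 12.1.2 does not say whether four months means response status at that time or best response by that time.

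**Working it through.** **The plan's own figure.** The plan gives no operating characteristics for the marker test or the response interval. Its one design figure, 83% power for PFS, can be reproduced. With exponential PFS, S(2 months) = 0.50 under a 2.0-month median and 0.5^(2/3.5) = 0.673 under a 3.5-month median. Then Φ((0.673 − 0.50)/√(0.673 × 0.327/37) − 1.2816) = 83.2%. Neither issue here touches it.

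**Why pairing matters.** On the log scale with equal variances, Var(after − before) = 2σ²(1 − ρ), where ρ is the within-patient correlation. A test that treats the samples as independent uses 2σ². Without baseline selection, a two-sided 0.10 z-test with the wrong variance has true level 2Φ(−1.645/√(1 − ρ)). At ρ = 0.3 this is 2Φ(−1.97) ≈ 0.05, and at ρ = 0.5 it is 2Φ(−2.33) ≈ 0.02. The rank sum test should behave similarly, becoming conservative as ρ rises. Selecting patients on a high baseline adds regression to the mean, which pushes rejection rates up for any before/after test.

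**Simulation.** The document gives no marker SD, correlation, elevation cut-off or number of patients with raised markers, so every input is an assumption:
- 20 patients; bivariate normal log markers with SD 1.5; ρ = 0.3, 0.5, 0.7 or 0.9 before selection.
- Baseline unselected, or drawn only from above the population 25th percentile or median.
- Two-sided 0.10; normal approximation with continuity correction; 10,000 runs per setting.
- Rank sum on raw before and after values; signed-rank on raw within-patient differences.

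Type I error (no true change), rank sum / signed-rank:

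| Baseline | ρ = 0.3 | ρ = 0.5 | ρ = 0.7 | ρ = 0.9 |
|---|---|---|---|---|
| No selection | 0.05 / 0.09 | 0.03 / 0.10 | 0.01 / 0.10 | <0.001 / 0.10 |
| Above 25th percentile | 0.21 / 0.18 | 0.11 / 0.15 | 0.03 / 0.12 | 0.001 / 0.10 |
| Above median | 0.65 / 0.45 | 0.42 / 0.33 | 0.17 / 0.21 | 0.01 / 0.13 |

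Signed-rank is nearer to 0.10 in 10 of the 12 settings. Rank sum is nearer in two: above the 25th percentile at ρ = 0.5, and above the median at ρ = 0.7.

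Power for a true 40% fall, no selection:

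| Test | ρ = 0.3 | ρ = 0.5 | ρ = 0.7 | ρ = 0.9 |
|---|---|---|---|---|
| Rank sum | 23% | 20% | 15% | 10% |
| Signed-rank | 29% | 36% | 49% | 86% |

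With selection at ρ = 0.7, the rejection rates are 52% (rank sum) and 65% (signed-rank) above the 25th percentile, and 82% and 81% above the median. These are not a fair power comparison, because neither test holds 0.10 in those settings.

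**Response rate.** Clopper-Pearson limits, taking all 37 patients as the denominator (Section 12.2 maximum):

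| Responders | 90% | 95% |
|---|---|---|
| 2/37 | 1.0–16.1% | 0.7–18.2% |
| 4/37 | 3.8–23.1% | 3.0–25.4% |
| 6/37 | 7.3–29.5% | 6.2–32.0% |

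The lower limit moves by 0.3 to 1.1 points and the upper by 2.1 to 2.5. The effect of the time point cannot be computed from the document.

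**The case against.** The strongest reply on the markers is that this is terminology. The same sentence sets a paired t-test and refers to the differences, so the intended test can be recovered and a literal unpaired analysis is unlikely. That is fair, and it is a reason for a low rating. It does not remove the error, because no other text names the right test.

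The second reply is that the plan excludes the unselected population, so the rows showing pure conservatism and lost power apply only if nearly all patients have raised markers. This stands. With selection, the error can go either way, and its size rests on inputs that the document does not supply.

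Third, renaming the test does not restore the level. Under selection, signed-rank on raw differences gives 0.10 to 0.45. On log differences it is worse: 0.12–0.30 above the 25th percentile and 0.19–0.72 above the median. This also stands. The reason for the change is that the data are paired; the simulated levels should not be read as the gain from it.

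On response, the endpoint is secondary and has no decision rule, so the confidence level affects only presentation. Section 10.1.1 also limits who is evaluable for response, so the denominator may be below 37. With scans every two 28-day cycles, the second reassessment falls near 16 weeks, so four months roughly matches a scheduled scan. That does not settle status at versus best by four months, nor does it reconcile 95% with 90%.

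**Conclusion.** Both points hold, and both are minor. The named fallback is an independent-samples test applied to paired data, probably a slip for the signed-rank test. Applied literally, its level is not controlled at 0.10: under the assumed inputs it ranges from below 0.001 to 0.65, with the direction set by the unknown correlation and elevation cut-off. The 95% and 90% levels for the response rate contradict each other, which moves the exact limits by 0.3 to 2.5 percentage points in the cases shown. The time points may conflict as well, but the text can be read either way. The textual errors are certain; the simulated sizes are illustrative. The primary PFS test, its α and its power do not change.

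**What to change.** In Section 12.1.2, replace the rank sum test with the Wilcoxon signed-rank test on the within-patient differences. In both the Synopsis and Section 12.1.2, state one confidence level and one assessment time point for the response rate, and say whether the time point means response status then or best response by then.

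The same edit could usefully settle three related gaps: the scale of the differences (raw or log), the sidedness of the 0.10 marker test, and the mismatch between the marker analysis in the Synopsis and that in Section 12.1.2. A sentence should note that, because patients are selected for raised markers, a fall may partly reflect regression to the mean whichever test is used.

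The cost is wording only, with no added data, visits or patients.
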